9.1. Disposition of Subjects and Withdrawals

All patients enrolled in the study will be accounted for. Descriptive summaries of population data will be provided overall, by randomization stratum, and by dose group; these will include

- The frequency and percent of patients in each analysis population, sex and age distribution
- The disposition of patients (including number of patients enrolled, number of patients randomized, number of patients treated, number of completers)
- study withdrawals by reason of withdrawal

9.2. Protocol Deviations

Protocol deviations will be documented throughout the study, and checked for on complete data for each patient by manual review as well as by electronic validation checks.

The final decision regarding inclusion/exclusion of patients from the analysis sets will be taken based on protocol adherence reports during data review meetings before database lock, data release and analysis, applying the definitions in section 7.

Major protocol deviations will be summarized by type of deviation and by dose group. Individual patients with these protocol deviations will be listed.

9.3. Demographics and Other Baseline Characteristics

Descriptive summaries of the demographic and other baseline characteristics will be completed for the populations specified below, overall and by dose group. Some particular tables will be repeated also by randomization stratum and/or by CIDP variant. Baseline tables include:

- Demographics (SAF, FAS, PP)
 Age, Gender, Race/Ethnicity, Height, Weight, BMI
 These parameters will also be summarized by investigational site
- Medical History (SAF)
 Medical history will be coded with the Medical Dictionary for Regulatory Activities (MedDRA, according to the version specified in the Data Management Plan). Incidences of findings in medical history will be summarized by MedDRA system organ class (SOC) and preferred term
- Prior and Concomitant Medications (SAF)
 Medications will be coded using the WHO Drug Dictionary (according to the version specified in the Data Management Plan). Incidences of prior and concomitant medications will be summarized by ATC level 2 and ATC level 4
- Screening Physical Examination
- · ECG at screening

(PT)

- Disease status (FAS) at screening:
 Adjusted INCAT disability score, I-RODS disability score, grip strength, MRC sum score, modified
 FSS (fatigue scale), NCS (electrophysiological recordings)
- Deterioration after the wash-out phase:

Any deterioration after the wash-out phase will be listed. The frequencies of deteriorations after the wash-out phase will be presented by dose group and category (Patients' Global Impression of Change, adjusted INCAT disability score, grip strength, I-RODS) as well as in total.

9.4. Measurement of Treatment Compliance

The following parameters will be listed and summarized per patient and/or per infusion:

- Body weight
- Actual dose (total and per kg body weight, based on the latest available weight measurement)
- Total dose of NewGam administered
- Total number of infusions administered
- Total volume of solution administered
- Infusion times
- Overall amount of product administered (only included in data listings)
- Infusion rates

Deviations from the planned treatment schedule will be summarized by counting the number of infusions that deviate from the scheduled intervals by more than 4 days, and by listing all cases with more than 4 days deviation individually.

10. Efficacy Analysis

The primary objective of this study is to confirm the efficacy of NewGam in patients with CIDP that were observed in published clinical studies by evaluating the proportion of responders in the 1.0 g/kg dose group.

This study will furthermore compare all efficacy endpoints between the different dosing groups.

Formal planned analyses are described below. It may be necessary for additional exploratory analyses to be performed after the results from the planned analysis are completed; in this case full details of additional analyses will be given in the CSR.

The evaluation of the primary endpoint will be performed for the FAS and for the PPS. The evaluation of secondary endpoints will be performed for the FAS, and in addition for the PPS in case the two populations differ by more than 5%. The FAS analysis is considered to be the primary assessment of efficacy, and will be presented first in the report.

10.1. Primary Efficacy Variable Analysis

The primary efficacy variable is the proportion of responders in the 1.0 g/kg NewGam arm at Week 24 (Termination Visit) relative to baseline (Week 0). A responder being defined as a patient with a decrease of at least 1 point on the adjusted INCAT disability score.

Confirmatory statistical testing of the primary endpoint will be done by constructing the 95% Wilson-Score confidence interval for the proportion of responders, and comparing the lower confidence limit with the predefined threshold of 0.42. This corresponds to a one-sided test of the following pair of hypotheses at the α =0.025 confidence level.

 H_0 : R < 0.42

 $H_1: R \ge 0.42$

Where *R* is the proportion of responders i.e. the number of patients in the FAS who are responders according to the abovementioned definition, divided by the total number of patients in the FAS.

This evaluation will also be presented for the PPS to assess the robustness of the primary study endpoint with respect to protocol deviations.

To assess and compare the primary efficacy endpoint also between the different dose groups, and also between the randomization strata (by dose group and over all dose groups) the proportion of responders will be presented side-by-side, including the 95% confidence intervals.

The time to first response and time to first worsening will be examined and presented by means of a Kaplan-Meier analysis.

Additional analyses, such as logistic regression- will be deployed to further examine any noteworthy differencesin an exploratory manner. The logistic regression model for analysis of response will include dose group, randomization stratum and CIDP variant (typical vs. atypical) as factors and baseline score as covariate. Odds ratios will be calculated to compare response rates between the factor levels, these will be presented together with 95% confidence intervals.

Moreover the proportion of responders after having provided rescue medication will be calculated with respect to all patients who received rescue medication and will be presented by dose group and overall, together with 95% confidence intervals.

10.2. Secondary and Exploratory Efficacy Variable Analysis

All efficacy endpoints detailed in section 3.2 will be summarized by means of descriptive statistics, presented graphically as appropriate, and listed in full detail. Tables and graphs will allow for direct comparison of the different dose groups. If data are tabulated by dose group, the presentations will also include a total category, summarizing the data of all subjects in any of the dose groups. Tables for changes from baseline will include 95% confidence intervals of the mean for continuous secondary endpoints (I-RODS total score; grip strength; MRC sum score; FSS total score; NCS measurements; QoL scores) and 95% confidence intervals for the median for ordinal scales (INCAT disability sore, PI-NRS), calculated with PROC univariate option CIQUANTDF.

Similar analyses as for the primary endpoint will be performed for response variables defined based on secondary endpoints (I-RODS, grip strength, MRC sum score). These will include analysis of response rates and 95% confidence intervals, logistic regression models using the same factors as for the primary endpoint, Kaplan-Meier analyses for time to response and time to first worsening and response rates after having provided rescue medication.

Moreover, ANCOVA models will be applied for continuous secondary endpoints (I-RODS total score; grip strength; MRC sums score; FSS total score; NCS measurements; QoL scores). These ANCOVA models for changes from baseline to end of study will include dose group, randomization stratum and CIDP variant as factors and baseline value of the score/measurement as covariate. ANCOVA models will be used for calculation of least square means in various subgroups as well as for calculation of difference in least square means between the factor levels. All least square means will be presented together with 95% confidence intervals.

Any deterioration during the dose evaluation phase will be listed. Moreover, deteriorations during dose evaluation will be presented by dose group and by their effect on subject disposition (discontinuation, rescue medication).

11. Safety and Tolerability Analyses

The analysis of safety assessments in this study will be presented for the SAF.

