3.1.2 Secondary Endpoints

Efficacy:

- Proportion of responders in the 0.5 g/kg and 2.0 g/kg NewGam arms at Week 24 relative to baseline at Week 0 compared to the 1.0 g/kg arm, based on the adjusted INCAT disability score
- Proportion of responders in the 0.5 g/kg and 2.0 g/kg NewGam arms at Week 24 relative to baseline at Week 0 compared to the 1.0 g/kg arm, based on the grip strength (Martin Vigorimeter) using the previously published minimum clinically important difference (MCID) cut-off of 8 kPa.[26]
- Proportion of responders in the 0.5 g/kg and 2.0 g/kg NewGam arms at Week 24 relative to baseline at Week 0 compared to the 1.0 g/kg arm, based on the I-RODS scores using the MCID concept related to the varying standard errors (MCID-SE) as recently demonstrated.[27]
- Time to first confirmed worsening on the adjusted INCAT disability scale by at least 1 point from the value at Baseline
- Mean change from Baseline (Week 0) to Termination Visit in
 - grip strength of both hands (assessed by Martin Vigorimeter) Inflammatory Rasch-built Overall Disability Sum Score (I-RODS using the concept of MCID-SE as recently reported; [Appendix 1](#)) and number of improvers
 - sum of the distal evoked amplitude of 4 right sided and 4 left sided motor nerves (peroneal, tibial, ulnar and median)
 - Pain Intensity Numeric Rating Scale (PI-NRS)
- Time to first confirmed worsening on the I-RODS scale
- Time to 1 point decrease (improvement of disability) in adjusted INCAT disability score
- Time to decrease in I-RODS scores

¹ The adjusted INCAT score is identical to the original INCAT disability score with the exception that upper extremity score changes from 0 (normal) to 1 (minor symptoms) or from 1 to 0 are excluded in determining the adjusted score, given that these changes are not considered clinically meaningful.

Safety:

Throughout the entire 24-week Dose-evaluation Phase:

- Occurrence of all adverse events (AEs)
- Short term tolerance parameters including vital signs
- Physical/neurological examination
- Laboratory parameters (hematology and clinical chemistry) and tests for viral safety
- Standard ECG (only at screening visit)

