3.2.2. Secondary and Exploratory Target Variables

Efficacy

- Proportion of responders in the 0.5 g/kg and 2.0 g/kg NewGam arms at Week 24 relative to baseline at Week 0 compared to the 1.0 g/kg arm, based on the adjusted INCAT disability score
- Proportion of responders in the 0.5 g/kg and 2.0 g/kg NewGam arms at Week 24 relative to baseline at Week 0 compared to the 1.0 g/kg arm, based on the grip strength (Martin Vigorimeter) using the previously published minimum clinically important difference (MCID) cut-off of 8 kPa
- Proportion of responders in the 0.5 g/kg and 2.0 g/kg NewGam arms at Week 24 relative to baseline at Week 0 compared to the 1.0 g/kg arm, based on the I-RODS scores using the MCID concept related to the varying standard errors (MCID-SE) as recently demonstrated (please refer to protocol)
- Time to first confirmed worsening on the adjusted INCAT disability scale by at least 1
 point or more from the value at Baseline
- Mean change from Baseline (Week 0) to Termination Visit in
 - grip strength of both hands (assessed by Martin Vigorimeter)
 - Inflammatory Rasch-built overall disability sum score (I-RODS using the concept of MCID-SE as recently reported; Appendix 1) and number of improvers
 - sum of the distal evoked amplitude of 4 right sided and 4 left sided motor nerves (peroneal, tibial, ulnar and median)
 - Pain Intensity Numeric Rating Scale (PI-NRS)
- Time to first confirmed worsening on the I-RODS scale
- o Time to 1 point decrease (improvement of disability) in adjusted INCAT disability score
- Time to decrease in I-RODS scores
- o Mean change from baseline (Week 0) to Termination Visit in:
 - modified Fatigue Severity Scale (FSS)
 - SF-36 Health Survey physical composite score (PCS), mental composite score (MCS) and their 8 health domains
 - Additional nerve conduction studies (NCS) analyses (e.g. individual nerve analysis)
- o For MRC the following will be done:
 - Time to decrease in MRC sum score to or below baseline value after temporary improvement (increase)
 - mean change from baseline (Week 0) to Week 12 and to Termination Visit
 - number of improvers by at least 4 points from baseline (Week 0) to Week 12
 and to Week 24

Safety:

- o Throughout the entire 24-week Dose-evaluation Phase:
- Occurrence of all adverse events (AEs)
- Short term tolerance parameters including vital signs
- Physical/neurological examination

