7.1. Subgroups

In addition to combined presentations over all strata, evaluation of the primary endpoint will be presented for each randomization stratum (prior treatment with Immunoglobulins or Corticosteroids) separately to facilitate the identification of noteworthy differences in the clinical responses between these two groups.

The different CIDP variants eligible for enrollment, such as Multifocal Acquired Demyelinating Sensory And Motor Neuropathy (MADSAM) or pure motor CIDP, will be compared with respect to dose group and proportion of response as well.

Additional analyses, such as logistic regression or ANCOVA, will be deployed for primary and secondary endpoints to further examine differences between subgroups in an exploratory manner. The ANCOVA models will also be used for least square means calculation including 95% confidence intervals in various subgroups (see section 10.2).

8. General Issues for Statistical Analysis

Descriptive summaries will be presented for each of the primary, secondary and exploratory variables. In general, summaries will be completed for all patients overall and by dose group, and the data will be presented by means of standard summary statistics according to the different types of data:

- Binary data (whether or not an event has occurred): counts and proportions
- Count data (the frequency of an event in a set time period): rate (count per unit time)
- Continuous data (measurements on a continuous scale, including quasi-continuous variables): arithmetic mean, standard deviation, median, minimum, maximum
- Scales data (Ordinal and Non-ordinal): absolute and relative frequencies
- Time-to-event data (how long it takes to observe the outcome of interest: time to event or last evaluation (censored data in case patients are lost to follow-up) and event rate). These parameters might not be tabulated separately, but can be included as an inset into a Kaplan-Meier plot of the product-limit survival function estimates.

Additional descriptive and exploratory statistics, such as geometric means, quartiles or confidence intervals, are included as appropriate. If not mentioned otherwise, confidence intervals are to be understood as two-sided, 95% confidence intervals.

In general the denominator for calculating percentages will be the total number of patients in the analysis population unless otherwise specified.

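### Pain (PI-NRS) is a secondary mean-change endpoint, but SAP 10.2 specifies no between-dose estimate with a confidence interval and no baseline-adjusted comparison for it

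*SAP*

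**What the plan says.** Protocol 3.1.2 lists PI-NRS among the secondary endpoints, under change from baseline. SAP 3.2.2 repeats this under the lead-in "Mean change from Baseline (Week 0) to Termination Visit in". The secondary items under that lead-in are grip strength, I-RODS, the sum of the distal amplitudes, and PI-NRS.

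SAP 10.2 then sorts the variables. Those it calls continuous get a 95% interval for the mean change. The two it calls ordinal get "95% confidence intervals for the median for ordinal scales (INCAT disability sore, PI-NRS), calculated with PROC univariate option CIQUANTDF". The modelling paragraph reads "ANCOVA models will be applied for continuous secondary endpoints (I-RODS total score; grip strength; MRC sums score; FSS total score; NCS measurements; QoL scores", and these models supply the "difference in least square means between the factor levels". A third paragraph gives response rates, logistic regression and Kaplan-Meier analyses to "response variables defined based on secondary endpoints (I-RODS, grip strength, MRC sum score". PI-NRS appears only in the median-interval list.

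Two general statements also bear on pain. SAP 8 assigns to rating scales "Scales data (Ordinal and Non-ordinal): absolute and relative frequencies". The opening of SAP 10 says "This study will furthermore compare all efficacy endpoints between the different dosing groups".

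**The concern.** The stated endpoint and the specified analysis do not match. The endpoint is a mean change; the only interval named for it is for a median within each arm. A median interval in each of three arms does not give a difference between doses, and it makes no use of the baseline pain score.

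The secondary objectives are about how the lower and higher doses compare with 1.0 g/kg. For pain, the reader of the study report would have summaries side by side but no pre-specified estimate of how far apart the doses are or how uncertain that distance is. Any such estimate produced later would count as unplanned under SAP 5.2 and would carry less weight.

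**Working it through.** **The plan's own figures.** The documents give no sample size, standard deviation or target difference for pain. Their only sample-size figure is for the primary endpoint: 62 evaluable patients in the 1.0 g/kg arm. It reproduces. With n = 62, the 95% Wilson lower limit first exceeds 0.42 at 34 responders, and the exact binomial power at a true rate of 0.60 is 83.1%. With n = 61 the power is 79.2%, and it stays at or above 80% at every size checked from 62 to 72. The figure matters here only because it fixes the arm sizes. At 1:2:1, 140 enrolled gives 35/70/35 and 124 evaluable gives 31/62/31.

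**Coverage of each item in SAP 10.2.**

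| Item | Status in protocol 3.1 | CI for mean change | ANCOVA | Responder model |
|---|---|---|---|---|
| Grip strength | secondary | yes | yes | yes |
| I-RODS | secondary | yes | yes | yes |
| Sum of distal amplitudes (under NCS) | secondary | yes | yes | no |
| **PI-NRS** | **secondary** | **no (median)** | **no** | **no** |
| Modified FSS | exploratory | yes | yes | no |
| MRC sum score | exploratory | yes | yes | yes |
| SF-36 scores | exploratory | yes | yes | no |

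Three of the four secondary mean-change items are modelled; PI-NRS is not, while three exploratory scales are. INCAT, the other scale given a median interval, has its own responder definition (SAP 8.4) and its own logistic and Kaplan-Meier analyses (SAP 10.1). Pain has no such alternative.

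**What the median interval delivers.** A distribution-free 95% interval for a median runs between two order statistics. Taking the narrowest symmetric pair with binomial coverage of at least 95%:
- n = 35: 12th and 24th values (coverage 95.9%)
- n = 70: 27th and 44th values (coverage 95.9%)

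PI-NRS is an 11-point scale from 0 to 10 (protocol 7.2.3.3). If it is scored in whole numbers, the changes, and so the interval ends, are whole numbers too. The intervals are valid for each arm but coarse, and they contain no contrast.

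**What a direct comparison would deliver, in SD units.** For a difference of two means with a common standard deviation, the 95% half-width is 1.96 × √(1/n₁ + 1/n₂):
- 35 vs 70: 1.96 × 0.2070 = 0.41 SD
- 31 vs 62: 1.96 × 0.2200 = 0.43 SD

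The difference detectable with 80% power at two-sided 5% is (1.96 + 0.84) times the same root, that is 0.58 SD and 0.62 SD.

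In ANCOVA the relevant SD is the residual one after adjustment for baseline. If that SD were 2 to 3 points (an assumption; the documents give none), the half-width for 35 vs 70 would be 0.41 × 2 = 0.8 to 0.41 × 3 = 1.2 points.

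**The case against.** The best defence is that the choice follows a readable rule. SAP 10.2 treats INCAT and PI-NRS as ordinal, and summed or measured quantities as continuous. PI-NRS is a single bounded item; the modified FSS is a Rasch-built sum (protocol 7.2.3.2) and the MRC score is a 0 to 60 sum. A median is a respectable summary for a single-item scale. The protocol synopsis and 9.2.2 promise only descriptive statistics for this endpoint, so leaving it out of an exploratory model breaks no protocol commitment. This stands, and it limits the weight of the point. It does not remove the mismatch: if pain is to be treated as ordinal, the mean-change wording is wrong and an ordinal between-dose estimate is still absent.

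SAP 7.1 could also be read as covering pain, since it announces exploratory logistic regression or ANCOVA for primary and secondary endpoints. But for the ANCOVA least square means it refers to 10.2, and the list there omits PI-NRS.

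Three stronger readings are tempting and are not supported:

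- *No dose comparison of pain is planned.* SAP 8 plans summaries by dose group, and SAP 10.2 plans tables and graphs that set the dose groups side by side. A descriptive comparison is planned.
- *The mean change will not be estimated at all.* SAP 10.2 says every endpoint in 3.2 will be summarized descriptively, and the median interval is an addition to those tables. Because SAP 8 gives means to quasi-continuous variables and frequencies to scales, it is unclear whether a mean will be shown. That is an ambiguity, not an omission.
- *A real dose effect on pain would be invisible.* One could set the power of an ANCOVA test against the chance that two median intervals fail to overlap, and the contrast would look large. The SAP proposes no such overlap rule, and the rule is strict for any statistic. Even for two separate mean intervals with equal SDs, non-overlap needs a difference of 1.96 × (1/√35 + 1/√70) = 1.96 × 0.2886 = 0.57 SD, against 0.41 SD for a direct interval. Such a contrast also rests on assumed pain SDs.

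**Conclusion.** The point holds as an internal inconsistency with a practical consequence. A secondary endpoint worded as a mean change has a median as its only specified interval, and it alone among the four secondary mean-change items has neither an interval for the mean nor a model. The SAP's stated intention to compare all efficacy endpoints between doses is met for pain only descriptively.

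The consequence is limited. The secondary dose comparisons are descriptive or exploratory throughout, so neither the primary test nor any confirmatory claim is touched. The lost precision cannot be given in pain points without a PI-NRS SD. The 0.41 SD half-width describes what the added comparison would offer, assuming equal SDs and complete data in 35 and 70 patients.

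The status of PI-NRS is itself unsettled: it is secondary in protocol 3.1.2, but protocol 7.2.3.3 places it among the exploratory assessments.

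**What to change.** In SAP 10.2:

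1. Add PI-NRS change to the variables reported with a 95% confidence interval for the mean.
2. Add PI-NRS change to the ANCOVA list with the model already specified there: dose group, randomization stratum and CIDP variant as factors, baseline PI-NRS as covariate. Report the 0.5 versus 1.0 g/kg and 2.0 versus 1.0 g/kg differences with 95% confidence intervals, labelled exploratory.
3. Keep the median interval as a supplement for readers who prefer an ordinal summary.

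In addition, state once whether PI-NRS is secondary or exploratory, and bring protocol 3.1.2 and 7.2.3.3 into line.

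If the sponsor prefers to keep pain strictly ordinal, the alternative is to reword the endpoint and name an ordinal between-dose estimate, such as a Hodges-Lehmann difference or a proportional-odds model with baseline.

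The cost is two list entries and one more run of a planned analysis. PI-NRS is already collected at every visit, and SAP 8.4 already defines how changes in scales are taken when rescue treatment has been given. The change should be made before the blind is broken, so that the pain comparison counts as planned.
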